8.1.3 Definition of Unanticipated Problems (UP)

Unanticipated Problems Involving Risk to Subjects or Others

Any incident, experience, or outcome that meets all of the following criteria:

- Unexpected in nature, severity, or frequency (i.e. not described in study-related documents such as the IRB-approved protocol or consent form, the investigators brochure, etc)
- Related or possibly related to participation in the research (i.e. possibly related means there is a reasonable possibility that the incident experience, or outcome may have been caused by the procedures involved in the research)
- Suggests that the research places subjects or others at greater risk of harm (including physical, psychological, economic, or social harm).

8.2 Classification of an Adverse Event

8.2.1 Severity of Event

For AEs not included in the protocol defined grading system, the following guidelines will be used to describe severity.

- **Mild** – Events require minimal or no treatment and do not interfere with the participant's daily activities.
- **Moderate** – Events result in a low level of inconvenience or concern with the therapeutic measures. Moderate events may cause some interference with functioning.
- **Severe** – Events interrupt a participant's usual daily activity and may require systemic drug therapy or other treatment. Severe events are usually potentially life-threatening or incapacitating.

8.2.2 Relationship to Study Agent

For all collected AEs, the clinician who examines and evaluates the participant will determine the AE's causality based on temporal relationship and his/her clinical judgment. The degree of certainty about causality will be graded using the categories below.

- **Definitely Related** – *There is clear evidence to suggest a causal relationship, and other possible contributing factors can be ruled out. The clinical event, including an abnormal laboratory test result, occurs in a plausible time relationship to drug administration and cannot be explained by concurrent disease or other drugs or chemicals. The response to withdrawal of the drug (dechallenge) should be clinically plausible. The event must be pharmacologically or phenomenologically definitive, with use of a satisfactory rechallenge procedure if necessary.*
- **Probably Related** – *There is evidence to suggest a causal relationship, and the influence of other factors is unlikely. The clinical event, including an abnormal laboratory test result, occurs within a reasonable time after administration of the drug, is unlikely to be attributed to concurrent disease or other drugs or chemicals, and follows a clinically reasonable response on withdrawal (dechallenge). Rechallenge information is not required to fulfill this definition.*
- **Possibly Related** – *There is some evidence to suggest a causal relationship (e.g., the event occurred within a reasonable time after administration of the trial medication). However, other factors may have contributed to the event (e.g., the participant's clinical condition, other concomitant events). Although an AE may rate only as "possibly related" soon after discovery, it can be flagged as requiring more information and later be upgraded to "probably related" or "definitely related," as appropriate.*
- **Unlikely to be related** – *A clinical event, including an abnormal laboratory test result, whose temporal relationship to drug administration makes a causal relationship improbable (e.g., the event did not occur within a reasonable time after administration of the trial medication) and in which other drugs or chemicals or underlying disease provides plausible explanations (e.g., the participant's clinical condition, other concomitant treatments).*
- **Not Related** – *The AE is completely independent of study drug administration, and/or evidence exists that the event is definitely related to another etiology. There must be an alternative, definitive etiology documented by the clinician.*

8.2.3 Expectedness

[name] will be responsible for determining whether an AE is expected or unexpected. An AE will be considered unexpected if the nature, severity, or frequency of the event is not consistent with the risk information previously described for the study agent.

8.3 Time Period and Frequency for Event Assessment and Follow-Up

The occurrence of an AE or SAE may come to the attention of study personnel during study visits and interviews of a study participant presenting for medical care, or upon review by a study monitor. All AEs including local and systemic reactions not meeting the criteria for SAEs will be captured on the appropriate RF. Information to be collected includes event description, time of onset, clinician's assessment of severity, relationship to study product (assessed only by those with the training and authority to make a diagnosis), and time of resolution/stabilization of the event. All AEs occurring while on study must be documented appropriately regardless of relationship. All AEs will be followed to adequate resolution.

Any medical condition that is present at the time that the participant is screened will be considered as baseline and not reported as an AE. However, if the study participant's condition deteriorates at any time during the study, it will be recorded as an AE. UPs will be recorded in the data collection system throughout the study.

Changes in the severity of an AE will be documented to allow an assessment of the duration of the event at each level of severity to be performed. AEs characterized as intermittent require documentation of onset and duration of each episode.

The PI will record all reportable events with start dates occurring any time after informed consent is obtained until 7 (for non-serious AEs) or 30 days (for SAEs) after the last day of study participation. At each study visit, the investigator will inquire about the occurrence of AE/SAEs since the last visit. Events will be followed for outcome information until resolution or stabilization.

All unresolved adverse events should be followed by the investigator until the events are resolved, the subject is lost to follow-up, or the adverse event is otherwise explained. At the last scheduled visit, the investigator should instruct each subject to report any subsequent event(s) that the subject, or the subject's personal physician, believes might reasonably be related to participation in this study. The investigator should notify the study sponsor of any death or adverse event occurring at any time after a subject has discontinued or terminated study participation that may reasonably be related to this study. The sponsor should also be notified if the investigator should become aware of the development of cancer or of a congenital anomaly in a subsequently conceived offspring of a subject that has participated in this study.

8.4 Reporting Procedures – Notifying the IRB

8.4.1 Adverse Event Reporting

Immediately report any harm experienced by a participant or other individual, whether occurring to a subject enrolled related to the human research procedure(s), and/or intervention(s) when ALL of the following three (3) conditions are met:

1. The harm is “unexpected” when its specificity and severity are not accurately reflected in the WCM consent document, Investigator’s Brochure (if applicable), or package insert (if applicable); AND
2. The harm is “related” or “possibly related”, where there is a reasonable possibility that the harm may have been caused by the research procedure(s), or intervention(s) AND
3. The harm suggests that the research places WCM subjects at greater risk of harm (including physical, psychological, economic or social harm) than was previously known or recognized.

If ALL of the three (3) conditions are met, submit the Immediate Report within 7 calendar days of PI awareness.

At the time of IRB Continuing Review, an Adverse Event Reporting Cumulative Table will be submitted listing adverse events from the study site that are both expected and unexpected and for which ANY of the following apply:

1. Severe or medically significant, but not immediately life-threatening; hospitalization or prolongation of hospitalization indicated; disabling; limiting self care activities of daily living (Grade 3)*
2. Life-threatening consequences; urgent intervention indicated (Grade 4)
3. Death related AE (Grade 5) Serious Adverse Event Reporting

8.5 Safety Oversight

It is the responsibility of the Principal Investigator to oversee the safety of the study at his/her site. This safety monitoring will include careful assessment and appropriate reporting of adverse events as noted above, as well as the construction and implementation of a site data and safety-monitoring plan. Medical monitoring will include a regular assessment of the number and type of serious adverse events.

Safety oversight will be under the direction of a Weill Cornell-based DSMB composed of individuals with the appropriate expertise, including hepatitis C and substance use disorder. The DSMB will meet at least semiannually to assess safety and efficacy data on each arm of the study. The DSMB will operate under the rules of an approved charter that will be written and reviewed at the organizational meeting of the DSMB. At this time, each data element that the DSMB needs to assess will be clearly defined. The DSMB will provide its input to the study sponsor (NIDA).

9 Statistical Considerations

9.1 Statistical and Analytical Plans (SAP)

We will examine a series of study outcomes in both study arms in order to evaluate the effectiveness of the Accessible Care (AC) intervention as compared with Usual Care (UC). Our three Aims are to compare hepatitis treatment, substance use, and HIV and HCV prevention outcomes in the two arms in order to answer three fundamental questions about the AC intervention: (1) Is it sufficiently safe and effective to allow active PWID in appreciable numbers to be successfully treated for hepatitis C? (2) Does it reduce substance use? (3) Does it reduce HIV and HCV risk behaviors? We will assess a multiplicity of outcome measures in order to fully describe the experience of participants in each arm.

9.2 Statistical Hypotheses

Specific Aim 1: Hepatitis C Outcomes.

Hepatitis C treatment engagement. We will assess the proportion of patients in each arm who (a) referred to a hepatitis C treatment provider, (b) attend an initial visit with a hepatitis treatment provider, and (c) complete a medical evaluation for antiviral treatment, including a history, physical examination, and laboratory evaluation. Proportions with 95% confidence intervals (CIs) calculated using the exact binomial method will be reported. Persons who are lost to follow-up will be considered in each analysis as not having reached the outcome, according to intent-to-treat principles.

Hepatitis C treatment success. We will compare the frequency of two hepatitis C treatment endpoints in the two arms in an intent-to-treat fashion, in order to evaluate the hypotheses that PWID in the intervention arm will be more likely than those in the control arm to begin treatment and achieve virologic responses to antiviral treatment for hepatitis C. The two endpoints will be defined as follows. Antiviral treatment initiation will be defined as physically receiving the first dose of antiviral medication. Sustained virologic response (SVR) will be defined as testing HCV RNA negative 12+ weeks after treatment completion.

Cost of intervention: The HCCC and the Clinician will log time spent providing services, excluding research activities. Costs will be assigned to staff time based on prevailing national wage rates. Patient time costs will also be estimated based on time spent with staff members and will be valued based on the minimum wage because most patients are likely to be unemployed. We will describe patient-reported health care visits, employment, and incarceration that will be used as inputs to future cost or cost-effectiveness studies.

Reinfection: We will report reinfection rates in all patients in both arms who achieve SVR using time-to-event methods. If 150 participants initiate antiviral therapy (50% overall) and 120 (80%) of those achieve SVR, with 2%/month attrition (21.5%/yr), we will have 198.3 person-years of follow-up when data collection is concluded, enough for a reasonably robust estimate.

Specific Aim 2: Substance use. We will report rates of addiction treatment entry and retention; changes in levels of self-reported alcohol and illicit drug consumption; and urine toxicology results. Outcomes will be examined at 3, 6, and 9 months after randomization, to assess the magnitude and durability of intervention effects. Effect sizes and 95% CIs will be reported.

Specific Aim 3: HIV and HCV risk behaviors. We will report changes in frequency of three injection related and three sexual HIV risk behaviors: (a) injection drug use, (b) use of a syringe previously used by another person, and (c) use of any injection equipment (cooker, cotton, mixing water, mixing syringe, rinse water) previously or simultaneously used by another person, (d) condomless vaginal or anal sex, (e) sex with multiple partners (≥ 2 in past 6 months), and (f) sex in exchange for money or drugs. Outcomes

will be reported at 3, 6, and 9 months after randomization, to assess the possibility of transient intervention effects.

Subgroup Analyses. We will conduct exploratory analyses of group assignment effects on study outcomes with 95% confidence intervals in the following subgroups that we hypothesize may differ in their ability to benefit from the AC intervention: (1) men and women (2) older and younger than sample median (3) homeless and housed (4) cocaine use and none (5) daily and less frequent illicit drug injection (6) heavy alcohol use (≥ 5 drinks/day) and less or none (7) health care utilization in past 6 months and none (8) psychiatric diagnosis and none. In the event of statistically significant interactions we will report treatment group assignment effects in subgroups only.

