Brief Summary	
The proposed study will examine the feasibility, acceptability, safety, effectiveness, and cost of an Accessible Care intervention for engaging people who inject illicit drugs (PWID) in hepatitis C care. Accessible Care for PWID is low-threshold care provided in programs designed specifically for PWID where they can comfortably access care without fear of shame or stigma. Accessible Care will be provided by co-locating a hepatitis treatment provider, together with a Hepatitis C Care Coordinator (HCCC), on-site at our collaborating needle exchange program. The proposed study will compare the effectiveness of Accessible Care with Usual Care (referrals to existing services) in facilitating linkage, engagement, and retention of PWID in care for hepatitis C, addiction, and HIV prevention. Our primary outcome is sustained virologic response, which constitutes virologic cure. Substance use and HIV and HCV risk behaviors are secondary outcomes. The Specific Aims of this study are to compare active PWID receiving Accessible Care or Usual Care on the following outcomes: 1. Hepatitis C Outcomes: (1a) Linkage and engagement in hepatitis C care, (1b) Successful hepatitis C treatment, (1c) Safety of hepatitis C treatment, and (1d) Rates of reinfection. 2. Substance use outcomes 3. Reductions in self-reported HIV and HCV risk behaviors. As all-oral regimens become available to patients who do not inject drugs, the substantial health disparities in hepatitis C already evident will become worse, as the haves are cured and the have-nots are not. Data are needed on effective methods to provide successful antiviral therapy to the core population affected by the epidemic, persons who are currently using illicit drugs, so that they, too, may benefit. Treatment can also help end the HCV epidemic by preventing onward transmission, but only if we have effective models for delivering treatment to people actively injecting drugs.

Phase	Clinical study phase 4
Objectives	The proposed study will compare the effectiveness of Accessible Care with Usual Care in facilitating linkage, engagement, and retention of PWID in care for hepatitis C, addiction, and HIV prevention.
Methodology	Open label; Randomized control
Endpoint	Our primary outcome is sustained virologic response (SVR), which constitutes virologic cure. Substance use and HIV and HCV risk behaviors are secondary outcomes.
Study Duration	4 years
Participant Duration	52 to 144 weeks

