Clinical data, including medication start and stop dates and doses, viral RNA levels, other laboratory test results, and adverse events, will be abstracted electronically from the WCMC electronic medical record or by requesting records from other facilities. The effectiveness of AC will be assessed and compared with Usual Care through formal intent-to-treat analyses comparing study endpoints. Semi-structured qualitative interviews will also be conducted with a theoretically sampled group of 60 participants 6 months after randomization, including some who dropped out or did not pursue treatment, to provide contextualized data on how the intervention worked, or didn't, and its strengths and weaknesses. All patients achieving SVR will be followed up with quarterly HCV RNA testing for the duration of the study to detect reinfections. The cost of the intervention in each arm will be estimated as a key component of assessing the feasibility of the interventions. While our program requires intensive effort by intervention staff, we anticipate that that the incremental cost of this effort will be well within the range of the current cost of hepatitis C treatment.

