Aim 1c. Cost of intervention: The HCCC and the Clinician will log time spent providing services, excluding research activities. Costs will be assigned to staff time based on prevailing national wage rates. Patient time costs will also be estimated based on time spent with staff members and will be valued based on the minimum wage because most patients are likely to be unemployed. We will describe patient-reported health care visits, employment, and incarceration that will be used as inputs to future cost or cost-effectiveness studies.

Aim 1d. Safety: Because concern about side effects has been cited as a reason not to treat PWID for hepatitis C, and because experience with these drugs in PWID has not been reported, we will report prospectively collected data on safety outcomes on all participants who receive antiviral therapy. All treatment-emergent side effects (e.g., fatigue, headache, nausea, insomnia, irritability, anorexia, diarrhea, constipation, etc.) will be tabulated, as will adverse events, including abnormalities in serum bilirubin, liver enzymes, infections, hospitalizations, and deaths), and any adverse effects requiring treatment discontinuation, according to OHRP152 and NIH153 guidelines. We will describe the frequency of side effects, adverse events, and treatment-limiting outcomes, among all study participants who received at least one dose of antiviral medication. If numbers permit, we will compare the rates in the two arms to see whether AC influences perceived side effects.

Aim 1e. Reinfection: We will report reinfection rates in all patients in both arms who achieve SVR using time-to-event methods. If 150 participants initiate antiviral therapy (50% overall) and 120 (80%) of those achieve SVR, with 2%/month attrition (21.5%/yr), we will have 198.3 person-years of follow-up when data collection is concluded, enough for a reasonably robust estimate.

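### The costing rule prices only logged service time and patient time, so it probably understates the provider cost of on-site Accessible Care by an unknown amount

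*Combined protocol and SAP*

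**What the plan says.** The costing method appears twice, in the same terms, in section 4.2.1 (Aim 1c) and section 9.2: "The HCCC and the Clinician will log time spent providing services, excluding research activities". The price attached is a wage: "Costs will be assigned to staff time based on prevailing national wage rates". One further component is priced: "Patient time costs will also be estimated based on time spent with staff members", valued at the minimum wage. Other resource use is collected but not priced in this study: "We will describe patient-reported health care visits, employment, and incarceration that will be used as inputs to future cost or cost-effectiveness studies".

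The Protocol Summary describes how Accessible Care is delivered: by "co-locating a hepatitis treatment provider, together with a Hepatitis C Care Coordinator (HCCC), on-site at our collaborating needle exchange program". Section 4.1 says what the cost is for: "The cost of the intervention in each arm will be estimated as a key component of assessing the feasibility of the interventions". It also anticipates that "the incremental cost of this effort will be well within the range of the current cost of hepatitis C treatment". No amount, threshold or decision rule accompanies either statement.

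**The concern.** The rule measures service delivered, while the intervention is staffed capacity at a particular site. A programme that adopts Accessible Care has to fund the hours during which the provider and the Hepatitis C Care Coordinator (HCCC) are present, whether or not participants attend. On its ordinary reading, time spent providing services does not include a slot left empty by a missed appointment. Such a slot adds nothing to patient time either, because that is derived from time with staff. Section 2.3 describes a population with competing priorities and many barriers to engagement, so unused time is foreseeable.

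The consequence is an awkward property. With staffing fixed, lower attendance lowers the reported cost although the bill is unchanged. What is at stake is whether the published Accessible Care cost tells a syringe programme what it would have to pay, which is the natural use of a cost described as part of feasibility.

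**Working it through.** There is no cost figure in the plan to reproduce. The documents give no wage, clinic hours, no-show rate, utilisation rate or non-labour share. The check is therefore a comparison of texts, followed by an illustration under stated assumptions.

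**Step 1. What the rule covers, set against what the on-site clinic uses.**

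| Input | Where described | Place in the costing rule |
|---|---|---|
| HCCC and Clinician time logged as service | 4.2.1 Aim 1c; 9.2 | Priced at wage rates |
| Patient time with staff | 4.2.1 Aim 1c; 9.2 | Priced at the minimum wage |
| Paid on-site time not used for service | Follows from co-location (Protocol Summary) | None stated; service time is not defined |
| Fringe and overhead | Not mentioned | None stated |
| Evaluation and treatment-monitoring blood draws by research staff | 7.1, Group A, items 5 and 8 | None stated; only the HCCC and the Clinician keep the log |
| Specimen transport, supplies, receipt of medication at the facility | 7.1, Group A, items 5, 7 and 8 (supplies implied) | None stated |
| Transit fare | 4.1, both arms | None stated |
| Usual Care on-site case manager | 7.1, Group B, item 4 | Not named as logging time |

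On the blood draws, section 1 lists venepuncture among the lead clinician's tasks, so some draws may be logged. Section 7.1 assigns the evaluation draw to other research staff and the monitoring tests to research staff (or commercial laboratories during the coronavirus period), without identifying those staff as the HCCC. Draws done by anyone outside the two logging roles are clinical labour that the rule does not reach.

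**Step 2. Direction.** Let H be paid non-research hours, u the share of H logged as service, and w the hourly wage.

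- Logged labour cost = w × u × H
- Full labour cost = w × H
- Ratio of full to logged = 1/u

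If s is the non-labour share of full provider-side cost, full provider cost = w × H / (1 − s), and its ratio to the logged labour cost is 1 / [u × (1 − s)]. This exceeds 1 whenever u < 1 or s > 0. The direction for the Accessible Care provider cost is therefore downward. Fringe is not in the formula and would raise the ratio further if the wage rates used exclude it.

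**Step 3. Illustrative size.** Every value of u and s here is an assumption.

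| Assumed u | s = 0 | s = 0.2 |
|---|---|---|
| 0.9 | 1/0.9 = 1.11 | 1/(0.9 × 0.8) = 1.39 |
| 0.8 | 1/0.8 = 1.25 | 1/(0.8 × 0.8) = 1.56 |
| 0.7 | 1/0.7 = 1.43 | 1/(0.7 × 0.8) = 1.79 |
| 0.5 | 1/0.5 = 2.00 | 1/(0.5 × 0.8) = 2.50 |

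**Step 4. The attendance property.** With H fixed, a fall in u from 0.8 to 0.5 multiplies the logged cost by 0.5/0.8 = 0.625, an apparent saving of 37.5%. The amount paid does not change.

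**Step 5. Between arms.** Let D be the full cost of Accessible Care minus that of Usual Care. The Accessible Care term is understated, but the Usual Care term is incomplete too, because neither the case manager nor the community clinics log time. Transit fare is given in both arms. The sign of the error in D cannot be determined from the documents.

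**The case against.** The strongest reply is that much of this rests on silence. The only activity that the rule excludes is research. Service time is undefined, and staff might reasonably log preparation, coordination and follow-up of missed visits under it. A reader might infer that idle time and non-labour inputs are set to zero; the documents do not say so, only that the stated rule gives them no place. The wage sentence likewise does not exclude fringe. This part of the objection stands, and it is itself a reason to define the term.

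Second, idle time is not documented. Section 7.1 describes scheduled visits, and no staffing level is given. Section 1 gives the lead clinician a research role as well, so unfilled time might go to research. This stands as a limit on size: the ratios above are an identity applied to assumed values and carry no information from the trial.

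Third, the benchmark in 4.1 concerns staff effort, which is what the plan costs, and no threshold is set. A reader might infer that a fuller cost would overturn the feasibility judgement, or that the incremental cost is understated. Neither follows, for want of a decision rule in the first case and for the reason in Step 5 in the second.

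Fourth, some listed inputs are not peculiar to Accessible Care. The Protocol Summary calls the blood draws standard of care for hepatitis C treatment, so treated Usual Care participants would incur similar tests, and part of the blood in 7.1 is drawn for research storage. Only the clinical share, and only inputs specific to the on-site clinic, belong in its cost.

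Finally, service-time costing is a legitimate perspective. That is so, but the plan states no perspective, and reporting both bases avoids having to choose. What survives is narrower: followed as written, the rule omits resources that an adopting site would fund.

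**Conclusion.** The point holds as an improvement to a descriptive outcome. The rule in 4.2.1 Aim 1c and 9.2 is likely to understate the provider cost of Accessible Care. The direction rests on the ordinary reading of service time and on at least some paid on-site time or some non-labour input falling outside the log. The amount is unknown; ratios of 1.25 to 2 illustrate assumed utilisation of 0.8 to 0.5 with no non-labour share, and should not be read as estimates.

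The documents do not support a conclusion that the between-arm incremental cost is biased in a known direction, or that the feasibility conclusion would change. The primary endpoint, sustained virologic response, is not affected.

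**What to change.** In 4.2.1 Aim 1c and 9.2:

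- Define what counts as service time, including how missed visits, preparation, travel and outreach are logged.
- Have the HCCC and the Clinician log total paid intervention hours (on site, plus any service work done elsewhere) and the research hours within them.
- Report Accessible Care cost per participant randomised on two bases: total minus research hours, and service time only. Give service hours divided by total minus research hours as utilisation.
- Value hours at wage plus fringe. Add clinical (non-research) phlebotomy time by research staff and the non-labour inputs specific to the on-site clinic.
- Apply the same cost categories to the Usual Care case manager where data allow. Otherwise label the result an Accessible Care provider cost and not an incremental cost.

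The price is slightly more logging on a log already kept, a short list of unit costs, and a less favourable Accessible Care figure. The service-time figure is still reported, so no information is lost. The hours are best recorded prospectively. One limit remains: empty slots that staff fill with research drop out of both bases, so research hours should be reported beside them.
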